8.1.9 Use of an Efficacy Subset of Subjects

Subjects randomized to study drug who were dispensed study product and do not have major protocol deviations will form the Per Protocol (PP) Population. The requirements for the PP Population are outlined in Section 8.4.4. Any additional major protocol deviations will be defined at the time of evaluability evaluation, the time between the database soft lock and hard lock before unblinding.

Excluding subjects who have major protocol deviations will decrease the variability in treatment response and will allow for a better determination of dose-response relationship of S5G4T-1, E-BPO Cream, 5%.

8.1.10 Active-Control Studies Intended to Show Equivalence

Not applicable to this study.

8.1.11 Examination of Subgroups

Subset analyses will be conducted for the ITT populations for the subgroups based on at least the following:

- Baseline Global Severity;

- Categorized as Baseline IGA = 3 (moderate) and Baseline IGA = 4 (severe); due to the inclusion criteria requiring subjects to have either a 3 or 4 IGA score at study entry other IGA response categories will not be presented
- Sex;
 - Male versus female subjects
- Age;
 - Dichotomized to less than the median age of ITT subjects and greater than or equal to the median age of ITT subjects
- Ethnicity;
 - Categorized as Hispanic or Latino and Not Hispanic or Latino; ethnicities of Not Reported and Unknown will not be included
- Race
 - Categorized as White and Non-White; subjects indicating more than one race category which includes both white and a non-white race will be summarized under the Non-White subgroup.

Subset analyses will be conducted on the variables absolute change from Baseline in inflammatory lesions at Week 12 as well as the dichotomized global severity score at Week 12. These analyses will contain only descriptive statistics.

8.2 Disposition of Subjects

The number of subjects included in each analysis population (randomized, ITT, Safety, and PP) will be summarized by treatment group and overall. The number of subjects completed and discontinued (including the reasons for discontinuation) will be summarized for each treatment group as well as by overall. The percentages will be calculated based on the number of randomized patients, unless otherwise specified.

8.3 Protocol Deviations

In order to define the PP Population, protocol deviations potentially influencing the evaluation of the primary efficacy endpoint will be defined as major deviations. The protocol deviations that will exclude a subject from PP are given in Section [8.4.4](#).

In case other deviations detected during the study conduct are considered to potentially influence the evaluation of the primary efficacy endpoint, these deviations will be documented prior to the database lock and the patients having these deviations will be excluded from the PP Population.

All protocol deviations will be reported to the sponsor and recorded throughout the study. Protocol deviations will not be entered into the database. SolGel will provide a list of protocol deviations to QST. A tabulation of protocol deviations will be presented in a data listing.

8.4 Data Sets Analyzed

Subjects will be presented/summarized based on the primary reason for exclusion. Below is the order to be used in summaries:

8.4.1 Randomized Population

All subjects who are randomized to study treatment will be included in the randomized population and will be analyzed according to the treatment group they were randomized. Listings will be provided for all randomized subjects.

8.4.2 Intent-to-Treat (ITT) Population

All subjects in the randomized population who are dispensed study product will be included in the ITT population and will be analyzed according to the treatment group they were randomized. All efficacy analyses will be presented using the ITT population.

8.4.3 Safety Population

All subjects in the randomized population who are presumed to have used the study product at least once and who provide at least one post-baseline safety evaluation will be included in the Safety population and will be analyzed according to the treatment they received. Presumed to have used study product will be defined as having at least one confirmed application of study medication. All safety analyses will be performed using the Safety population.

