19.1.4. Analysis Populations

Approximately 350 male and female patients at least 18 years of age with moderate or severe papulopustular rosacea with 3 or 4 [moderate to severe] on the IGA scale will be enrolled and randomized in the study with a 2:1 randomization ratio, it is anticipated that:

- 234 patients will be randomized to receive S5G4T-1, Encapsulated Benzoyl Peroxide (E-BPO) Cream, 5%
- 117 patients will be randomized to receive S5G4T-2, Vehicle Cream

The ITT population will consist of all randomized patients who were dispensed study product. The safety population will be comprised of all randomized patients who are presumed to have used the study product at least once and who provide at least one post-baseline safety evaluation.

An intent-to-treat (ITT) analysis will be conducted on all study patients. A per-protocol (PP) analysis will also be conducted. Patients will be eligible for the PP analysis if they complete the 12-week evaluation without noteworthy study protocol violations (i.e., any patient or investigator activity that could have possibly interfered with the therapeutic administration of the treatment or the precise evaluation of treatment efficacy). The PP population will include patients in the ITT population who do not meet any of the following criteria:

- Failed any of the inclusion/exclusion criteria;
- Have taken any interfering concomitant medications;
- Did not attend the Week 12 Visit;
- Missed more than 1 post baseline study visit prior to Week 12
- Have not been compliant with the dosing regimen (i.e., Patients may not miss more than five consecutive days of dosing and must take 80 to 120% of expected doses. The number of expected doses will be determined for each patient based on the length of their participation in the study);
- Out of visit window (\pm 4 days) at the 12-week Visit.

Patients that discontinue from the study due to an adverse event related to study treatment or documented lack of treatment effect will be included in the PP population. Data for these subjects will not be imputed by multiple imputation but rather their data will be imputed with values consistent with their status as treatment failures. Prior to breaking the blind, other additional criteria may be added to the list to accommodate for unforeseen events that occurred during the conduct of the trial that result in noteworthy study protocol violations.

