Table 14.2.15.1: Summary of RosaQoL Questionnaire Responses at Baseline and Week 12 (Intent-to-Treat Population)	117
Table 14.2.15.2: Summary of RosaQoL Questionnaire Responses at Baseline and Week 12 (Per-Protocol Population)	121
Table 14.3.0.1: Summary of Extent of Exposure (Safety Population)	122
Table 14.3.1.1: Summary of Cutaneous Safety and Tolerability Evaluations (Safety Population).....	123
Table 14.3.1.2.1: Summary of Treatment-Emergent Adverse Event Characteristics (Safety Population).....	131
Table 14.3.1.2.2: Summary of Treatment-Emergent Adverse Events by MedDRA System Organ Class and Preferred Term (Safety Population).....	133
Table 14.3.1.2.3: Summary of Treatment-Emergent Adverse Events by Severity (Safety Population)	134
Table 14.3.1.2.4: Summary of Treatment-Emergent Adverse Events by Relationship to Study Drug (Safety Population)	135
Table 14.3.1.3.1: Summary of Treatment-Emergent Serious Adverse Event Characteristics (Safety Population).....	136
Table 14.3.1.3.2: Summary of Treatment-Emergent Serious Adverse Events by MedDRA System Organ Class and Preferred Term (Safety Population).....	138
Table 14.3.1.3.3: Summary of Serious Treatment-Emergent Adverse Events by Severity (Safety Population)	139
Table 14.3.1.3.4: Summary of Treatment-Emergent Serious Adverse Events by Relationship to Study Drug (Safety Population).....	140
Table 14.3.1.4.1: Summary of Vital Signs (Safety Population)	141
Table 14.3.1.4.2: Shift Table of Vital Signs (Safety Population).....	146

Statistical Analysis Plan

Sol-Gel Technologies Ltd. SGT-54-02

Version: 1.0

Date: 02 MAY 2019

Table 14.3.1.5: Summary of Abnormal Physical Examination Findings by Visit (Safety Population)147

Table 14.3.1.6: Summary of Patient Global Impression of Treatment Side-Effects (PGI-SE) at Each Evaluation (Safety Population)148

Table 14.0.1: Summary of Subject Completion/Discontinuation
(All Randomized Subjects)

	E-BPO 5% Cream (N=xxx)	Vehicle Cream (N=xxx)	Total (N=xxx)
Completed Study			
Yes	xx (xx.x%)	xx (xx.x%)	xx (xx.x%)
No	xx (xx.x%)	xx (xx.x%)	xx (xx.x%)
Reason for Discontinuation			
Adverse Event	xx (xx.x%)	xx (xx.x%)	xx (xx.x%)
Lost to Follow-Up	xx (xx.x%)	xx (xx.x%)	xx (xx.x%)
Lack of Efficacy	xx (xx.x%)	xx (xx.x%)	xx (xx.x%)
Pregnancy	xx (xx.x%)	xx (xx.x%)	xx (xx.x%)
Protocol Violation	xx (xx.x%)	xx (xx.x%)	xx (xx.x%)
Withdrawal by Subject	xx (xx.x%)	xx (xx.x%)	xx (xx.x%)
Study Terminated by Sponsor	xx (xx.x%)	xx (xx.x%)	xx (xx.x%)

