Physician Decision	xx (xx.x%)	xx (xx.x%)	xx (xx.x%)
Worsening of Condition	xx (xx.x%)	xx (xx.x%)	xx (xx.x%)
Other	xx (xx.x%)	xx (xx.x%)	xx (xx.x%)

SOURCE: USERNAME\SPONSOR\PROJECT\JOBNAME (DATE,TIME)

Table 14.0.2.1: Summary of Subject Enrollment and Evaluability
(All Randomized Subjects)

	E-BPO 5% Cream (N=xxx)	Vehicle Cream (N=xxx)	Total (N=xxx)
Number of Randomized Subjects	xx	xx	xx
Number of Subjects Included in the ITT Population	xx (xx.x%)	xx (xx.x%)	xx (xx.x%)
Number of Subjects Excluded from the ITT Population	xx (xx.x%)	xx (xx.x%)	xx (xx.x%)
Reason Excluded from the ITT Population			
Not Dispensed Study Drug	xx (xx.x%)	xx (xx.x%)	xx (xx.x%)
Number of Subjects Included in the Safety Population	xx (xx.x%)	xx (xx.x%)	xx (xx.x%)
Number of Subjects Excluded from the Safety Population	xx (xx.x%)	xx (xx.x%)	xx (xx.x%)
Reasons Excluded from the Safety Population ^a			
No Documented use of Study Drug	xx (xx.x%)	xx (xx.x%)	xx (xx.x%)
No Post Baseline Safety Assessment	xx (xx.x%)	xx (xx.x%)	xx (xx.x%)
Number of Subjects Included in the PP Population	xx (xx.x%)	xx (xx.x%)	xx (xx.x%)
Number of Subjects Excluded from the PP Population	xx (xx.x%)	xx (xx.x%)	xx (xx.x%)
Reasons Excluded from the PP Population ^a			
Not Included in ITT Population	xx (xx.x%)	xx (xx.x%)	xx (xx.x%)
Violated Inclusion/Exclusion Criteria	xx (xx.x%)	xx (xx.x%)	xx (xx.x%)
Used Interfering Concomitant Medication	xx (xx.x%)	xx (xx.x%)	xx (xx.x%)
Did not Attend Week 12/ET Visit	xx (xx.x%)	xx (xx.x%)	xx (xx.x%)
Missed More Than 1 Post-Baseline Visit Prior to Week 12	xx (xx.x%)	xx (xx.x%)	xx (xx.x%)
Not Compliant with Dosing Regimen ^b	xx (xx.x%)	xx (xx.x%)	xx (xx.x%)
Week 12/ET Visit Out of Window (+/-4 days)	xx (xx.x%)	xx (xx.x%)	xx (xx.x%)
Other	xx (xx.x%)	xx (xx.x%)	xx (xx.x%)

^a Table includes primary reason (assigned in order presented in table) for reason subject was excluded.

^b Subjects lost to follow-up not included. A subject was considered compliant with the dosing regimen if the subject applied 80-120% of the expected number of applications and did not miss more than 5 consecutive applications while enrolled in the study.

SOURCE: USERNAME\SPONSOR\PROJECT\JOBNAME (DATE,TIME)

Table 14.0.2.2: Summary of Subject Evaluability by Analysis Center and Investigational Site
 (All Randomized Subjects)
 (Page 1 of xx)

Analysis Center	Investigational Site	Number Randomized	E-BPO 5% Cream			Vehicle Cream		
			ITT	PP	Safety	ITT	PP	Safety
xx	xx	xx	xx	xx	xx	xx	xx	xx

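### The Safety population requires a confirmed application and a post-baseline safety evaluation, so exposed patients may be left out of the adverse event tables because of what happened after exposure

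*SAP*

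**What the plan says.** SAP 8.4.3 and Protocol 19.1.4 both build the safety population from randomized patients "who are presumed to have used the study product at least once and who provide at least one post-baseline safety evaluation". The SAP then defines the first condition more tightly: "Presumed to have used study product will be defined as having at least one confirmed application of study medication". It goes on: "All safety analyses will be performed using the Safety population". The titles of the treatment-emergent and serious adverse event tables (14.3.1.2.1 to 14.3.1.3.4) name this population.

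The shell of Table 14.0.2.1 plans for both exclusions. One row is for subjects without documented use, and the next is "No Post Baseline Safety Assessment". A footnote says that each subject is counted under one primary reason, assigned in the order of the rows.

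SAP section 2 gives the SAP precedence where it differs from the protocol, so the confirmed wording would govern. SAP section 10, which lists departures from the protocol, does not mention it.

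**The concern.** A safety population should be fixed by exposure. Here an exposed patient can be removed by something that happens later, namely whether a safety evaluation followed and whether use could be confirmed. Some of those who miss both may have stopped because of the product.

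This matters more than usual because of how local reactions are recorded. Under Protocol 16.1 and 16.2, dryness, scaling, itching and burning/stinging become adverse events only if they lead to a pause in treatment, withdrawal from the study or a new concomitant medication. A patient who leaves over an early skin reaction is one of the few whose local reaction would reach the adverse event tables at all. At stake are the tabulated rates of treatment-emergent and serious events, the fatal-outcome and discontinuation rows, and the Fisher comparisons of SAP 8.8.2.

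**Working it through.** No figure in the plan depends on this definition, so the check is mainly a comparison of passages.

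**1. Can an event be known without a visit?** Yes. The first post-baseline visit is Week 2, Day 15 (± 3 days). Protocol 17.4 accepts events that the patient reports spontaneously. Protocol 17.5 and 17.7 have sites pass on serious events by telephone, email or facsimile.

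**2. Does such a report count as a post-baseline safety evaluation?** The documents do not say. Protocol 16 ties safety assessment, including adverse event reporting, to visits. SAP 7.2 lists adverse event reporting as one of the ways safety is assessed and does not mention visits. SAP 8.1.3 adds a further gap: early termination and unscheduled data before study day 8 are not analyzed, and nothing states whether such a visit still meets the condition.

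**3. What confirms an application?** This is also undefined. The diary is first reviewed at Visit 3 and first collected at Visit 4, when the first pump is also returned and weighed. For a patient who never comes back, confirmation would have to come from what the patient or someone else tells the site.

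**4. Who is kept under each reading?** Take patients who were dispensed product and attended no visit afterwards:

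| Patient | Evaluation means a visit | An adverse event report counts | Population defined by presumed use |
|---|---|---|---|
| Reports use and an event | out | in | in |
| Reports use, no event | out | out | in |
| Event reported by a third party, use not confirmed | out | out | in |
| No contact at all | out | out | in, unless non-use is documented |

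The first reading can drop a reporter together with the event. The second keeps that reporter but drops an equally exposed patient with nothing to report. Under both, membership depends on a post-exposure outcome.

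**5. Is the exclusion of known users intended?** Yes. Reasons are assigned in row order, and the row for missing use comes first. Anyone counted under "No Post Baseline Safety Assessment" therefore has documented use.

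**6. Is the rule consistent with the event rule?** No. SAP 8.8.2 treats an event as treatment-emergent unless the case report form marks it as before the first application. Exposure is thus presumed for the event but must be confirmed for the patient. An event can be treatment-emergent while its patient is outside every treatment-emergent table.

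**7. What is one patient worth?** Planned arms are 234 and 117 (SAP section 9).
- Active: 1/234 = 0.4%.
- Vehicle: 1/117 = 0.9%.
- SAP 8.8.2 tests terms reported by 1% or more of either arm. 1% of 234 is 2.34, so three active patients are needed; 1% of 117 is 1.17, so two vehicle patients are needed. One omitted reporter can therefore decide whether a term is tested.

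This shows scale only. The documents give no count of such patients, so no rate is projected.

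**The case against.** The strongest reply is that exclusion is not certain. A patient whose event is known to the trial has, by SAP 7.2, supplied a form of safety assessment. Other contacts also narrow the gap. Dryness, scaling and tolerability are rated at unscheduled visits too. Early terminators are to complete the Week 12 procedures. Protocol 13.2 requires follow-up contacts with anyone who discontinues for an adverse event. All of this stands, and it is why the point says *may*. It does not answer the second reading, where the silent user is the one dropped.

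A second reply is that nothing is hidden. SAP 8.4.1 promises listings for all randomized subjects, and these include treatment-emergent events, serious events and adverse event discontinuations. Table 14.0.1 shows discontinuations for adverse events by arm for all randomized subjects. Table 14.0.2.1 shows the exclusions themselves by reason and arm. This also stands. The rates and Fisher tests, however, come from the Safety population tables.

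Third, the confirmed-application condition mostly affects patients with no contact, who have no recorded event to lose; someone who telephones about a reaction to the cream has in effect reported use. This is largely right. SAP 8.1.2, which foresees an unknown first application date after loss to follow-up, adds little here, because it is a rule for flagging Baseline records and does not settle whether use is confirmed.

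Finally, presuming exposure adds patients without recorded events to the denominator and lowers the reported rates. That is true and is the price of the change.

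**Conclusion.** The point holds in a limited form. As written, the Safety population selects exposed patients on what happened after exposure, whichever way the undefined term is read. The step from presumed to confirmed use is an unlisted change from the protocol. A known event in a non-returning patient may be absent from the adverse event tables and tests, depending on that reading.

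A reader might infer two stronger conclusions, and the documents support neither. One is that such a patient is certain to vanish from the safety reporting. The term is open, and the listings and, for adverse event discontinuations, Table 14.0.1 would still carry the case. The other is that the active arm's event rates would be understated relative to vehicle. No passage gives the number of non-returning users or shows that they cluster in one arm, and SAP section 4 describes all three Phase 2 formulations as well tolerated.

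The size is therefore unknown, and it could be zero if every user has a post-baseline evaluation. The conclusion rests only on the wording of the definition and on at least one user not returning. It is a cheap improvement.

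**What to change.** In SAP 8.4.3 and Protocol 19.1.4 (and the matching synopsis text), before unblinding:

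- Define the Safety population as all randomized patients who used the product at least once. Restore presumed use: a patient who was dispensed product is presumed exposed unless non-use is documented, and any adverse event report after dispensing counts as evidence of use.
- Delete the evaluation requirement and the row "No Post Baseline Safety Assessment" from Table 14.0.2.1. Reword the remaining row as documented non-use.
- List the change in SAP section 10.

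Defining the term so that an adverse event report counts would not be enough, because silent users would still be dropped.

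The cost is a few sentences and one table row. By-visit tables show their own observed n without imputation, so they keep working as planned. The downside is that a few patients with no contact after dispensing enter the adverse event denominator and slightly lower the reported rates. Reporting their number by arm lets the reader judge the effect.

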8.4.4 Per-Protocol (PP) Population

All subjects in the ITT population who complete the Week 12 evaluation without noteworthy study protocol violations (i.e., any patient or investigator activity that could have possibly interfered with the therapeutic administration of the treatment or the precise evaluation of treatment efficacy) will be included in the PP population and analyzed according to the treatment group they received. The PP population will include subjects in the ITT population who do not meet any of the following criteria:

- Failed any of the inclusion/exclusion criteria;
- Have taken any interfering concomitant medications;
- Did not attend the Week 12 Visit;
- Missed more than 1 post-baseline study visit prior to Week 12;
- Have not been compliant with the dosing regimen (i.e., Patients may not miss more than five consecutive days of dosing and must take 80 to 120% of expected applications. The number of expected applications will be determined for each patient based on the length of their participation in the study);
- Out of visit window (± 4 days) at the 12-week Visit.

Subjects that discontinue from the study due to an AE related to study treatment or documented lack of treatment effect will be included in the PP population. Data for these subjects will not be imputed by multiple imputation but rather their data will be imputed with values consistent with their status as treatment failures. See Section 8.1.5 for additional detail. Prior to breaking the blind, other additional criteria may be added to the list to accommodate for unforeseen events that may occur during the conduct of the trial and result in noteworthy study protocol violations.

All efficacy analyses performed on the PP population will be according to the treatment they received.

8.5 Demographic and Other Baseline Characteristics

All Baseline summaries will be done on the ITT, PP, and Safety populations by treatment group and overall.

Sex (categorical), race (categorical), and ethnicity (categorical) will be summarized by counts and percentages. Age (continuous), height (cm) (continuous), and weight (kg) (continuous), and body mass index (BMI) (continuous) will be summarized with descriptive statistics.

Age will be calculated as the difference in days between the date of birth and the date of informed consent and converted to years by dividing the number of days by 365.25 and using a floor function to drop the decimal portion. In case the exact birth day is missing, day 15 will be used. The BMI will be calculated as weight (kg) divided by squared height (m^2).

Medical histories will be coded using the Medical Dictionary for Regulatory Activities (MedDRA) dictionary and presented in a by-subject listing.

The medical history data will be summarized with frequencies and percentages of patients with at least one medical history term reported, and patient frequencies and percentages on the System Organ Class (SOC) and Preferred Term (PT) levels. The number of events will also be summarized. The table will be sorted by overall descending frequency of SOC and then, within a SOC, by overall descending frequency of PT.

8.6 Prior and Concomitant Medications

Concomitant medications will be coded to preferred name and Anatomical Therapeutic Chemical (ATC) classification of ingredients using the World Health Organization (WHO) Drug Global Dictionary, Format B3, Version March 1, 2018.

Medications which start prior to first application will be considered prior medications. Ongoing medications and medications ending after the date of first application will be considered concomitant medications. If the date of first application is unknown and the medication is not listed as ongoing the interval will be considered “unknown”. If the date of first application is unknown and the medication is listed as ongoing the interval will be considered concomitant.

Incomplete medication start and end dates will be imputed as described in Section [8.1.5.3](#)

A summary of prior and concomitant medications will be provided.

A by-subject listing of all prior and concomitant medications will be presented for the Safety population.

